The study would utilize up to 400 volunteers (200 completers) recruited via an online commercial recruitment platform to participate in an online study. Volunteers will be asked to participate at two time-points. At time-point one, volunteers would be randomly assigned to complete one of two versions of HBMT. One version is designed to train the brain (rehearse and reinforce) to seek positive interpretations of ambiguous social cues and to inhibit thoughts and behaviors related to hostility. The second is a placebo version that is not expected to affect attitudes, cognitions, or behaviors. These versions were validated in a prior study (WRAIR #2574). Volunteers will also complete some brief surveys to assess state emotion, trait anger, and HAB. Volunteers will be asked to return between 24 and 96 hours later to complete another brief measure of HAB, state emotion, and a brief self-report survey about their online (public behavior only), driving, and other behaviors over the preceding 24 hours. We hypothesize that volunteers who receive the genuine training will display the less hostile bias and report lower anger and aggression in their daily behaviors when assessed at the second time-point.

If successful, these findings would provide evidence that HBMT is effective in affecting real-life behaviors and help convince potential stakeholders of the value of HBMT. Future research could validate effectiveness in operational units as well as with unhealthy populations (e.g., anger management groups). Future research could also test the effectiveness of HBMT on behavioral health outcomes for usage by clinicians and portable use by individuals with unhealthy hostile bias and problems with social aggression when isolated from traditional behavioral health care (e.g., far forward deployed units).

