Volunteer recruitment and data collection will be done online by ARL AI's and/or staff with assistance from volunteerscience.com (the online experimental platform). Volunteers will be recruited via Amazon Mechanical Turk (MTurk) to the experimental webpage and complete informed consent electronically. A description of this clinical trial will be available on <http://www.clinicaltrials.gov>. Additionally a copy of the informed consent may be posted to a public website no later than 60 days after enrollment is completed.

Time-point 1: Volunteers will be randomly assigned to complete either the real or fake HBMT. Volunteers will also complete a brief vignette reading HAB activity, a brief measure of trait (what is typical for them) aggression, and state (how they have felt recently) anger.

Time-point 2: Volunteers will be asked to return no sooner than 24 hours and no later than 96 hours from when they completed time-point 1 to complete a following up HAB assessment (second vignette interpretation task) and brief surveys asking about aggressive behaviors and state anger during the preceding 24 hour period.

Mechanism for inviting volunteers back to complete time-point 2: The two-time point nature of this study will be explained to volunteers in both the study advertisement and in the ICD.

Additionally, a feature on MTurk will allow the volunteerscience.com to send a daily e-mail to time-one volunteers inviting them back to time-point two. This can be done without MTurk revealing the e-mail addresses of the volunteers. The e-mail will remind volunteers to please return at any point between 24 hours and 96 hours from when they completed the first time-point.

Upon completion of each time-point, the webpage will thank volunteers for their participation. Volunteers will be paid part of the payment at the end of time-point one and the remaining payment after completing time-point two (see section 10.6).

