### 8.8 Study Procedure

The procedural flow of the experiment with estimated times for each step is outlined below. The study will not proceed until/unless the volunteer clicks that they have read the ICD and agree. The times provided are only estimates of the duration we anticipate the typical volunteer will use.

Time-point One:

- a. Volunteer arrives at study webpage and reviews ICD (estimated to take approximately 1-2 minutes)
- b. Volunteer completes trait anger questionnaire (1 minute)
- c. Volunteer Completed State Emotion Questionnaire (3 minutes)
- d. Volunteer reads instructions for real/fake HBMT (1 minute)
- e. Volunteer completes real/fake HBMT (15 minutes)
- f. Volunteer completes ACS Scale (set A) (10 minutes)
- g. Volunteer completes demographic items (< 1 minute)
- h. Volunteer is thanked for participation (< 1 minute)

Time-Point Two (24-96 hours later)-volunteers will received daily reminder e-mails via anonymous mturk.com functionality during interim.

- i. Volunteer arrives at study webpage and reviews ICD (same ICD as from time 1; estimated to take approximately 1-2 minutes).
- j. Volunteer Completes ACS (set B) (10 Minutes)
- k. Volunteer Completed State Emotion Questionnaire (3 minutes)
- l. Volunteer Completes State Measure of Aggression (10 Minutes)
- m. Volunteer is thanked for participation (< 1 minute)

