## 9 STATISTICAL METHODS AND DATA ANALYSIS

### 9.1 Analyses for Main Study Hypotheses

Between group differences (comparing real vs. fake HBMT) in the change in state anger and state HAB across time points (change from time-point one to time-point two) will be primarily assessed with a mixed-designs ANOVA. Between group differences in state aggression measured at time-point two will be assessed with a General Linear Models (GLM) analysis controlling for trait anger and demographics (age and gender).

We will also plot effect of group comparing real vs. fake HBMT and time between time-points (24-96 hours) on change scores (time 2 anger/aggression minus time 1 anger aggression) and analyze this using a linear regression with an interaction term.

Lower order effects will be tested using corrected Fishers LSD, Tukey, Scheffe, or other pairwise test as appropriate. Appropriate data-transformations may be used as necessary to satisfy significance test requirements. Lower order effects will also be assessed with pairwise dependent means t-tests. Age and gender will be controlled as covariates. Mediation analyses (if used) will be performed using non-parametric Monte-Carlo bootstrapping procedures using PROCESS (see Hayes, 2017).

We may use age, gender, and trait measures as control variables in analyses.

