## 13 APPENDICES

### Appendix A: Recruitment Materials

#### MTurk Advertisement

(Note: the field titles and sections are standardized on MTurk).

**Title:** Psychology Study: Help Scientists Test the Relationship Between a Vocabulary Task and How People Behave in Daily Life.

**Description:** This is a two part research study. At time-point one, you will fill out some brief personality surveys. You will also read several short scenarios and imagine how you would react and/or interpret these situations in real life. You will also complete a vocabulary task where you will sort word fragments based on type as quickly as you can. This will take approximately 30 minutes. You will be asked to return in 24-96 hours for part two where you will repeat a similar scenario reading activity as during time one and fill out a brief questionnaire about your recent behaviors. This second time-point will take about 25 minutes.

**Keywords:** Psychology, Study, Experiment, Science, Sorting, Reading

**Payment:** \$5 (\$3 at time-point one and \$2 at time-point two)

**Number of assignments per HIT:** 400

**Time Allotted Per Assignment:** 1 hour

**HIT Expires in:** [TBD]

**Auto-approve and pay workers in:** 8 hours

**Appendix B: Angry Cognitions Scale  
(ACS)**

**Directions:** Below are several scenarios followed by types of thoughts people often have in similar situations. For each scenario, imagine that what is being described has just happened to you. Then, read each thought and fill in the circle indicating how likely you would be to have that thought or one similar to it in that situation. There are no right or wrong answers and you are not being asked whether these thoughts are appropriate - only how likely you would be to have similar thoughts. Please respond to all of the thoughts for each scenario.

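### The delay analysis needs an aggression change score, but aggression is measured only at time-point two, so its aggression half cannot be run as written

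*Combined protocol and SAP*

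**What the plan says.** The second paragraph of Section 9.1 sets out the delay analysis. Its predictors are group (real or fake training) and the time between sessions, 24 to 96 hours. Its outcome and method are given as "change scores (time 2 anger/aggression minus time 1 anger aggression) and analyze this using a linear regression with an interaction term". The paragraph before it treats state aggression as a time-point-two measure and compares the groups with a general linear model (GLM) adjusted for trait anger, age and gender, with no baseline value.

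Section 8.8 lists the aggression form once, as step l of time-point two: "Volunteer Completes State Measure of Aggression (10 Minutes". The trait form at time-point one is step b: "Volunteer completes trait anger questionnaire (1 minute". The State Emotion Questionnaire appears at both time-points (steps c and k).

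The other descriptions of the visits are:

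- **Précis, time-point one:** "Volunteers will also complete some brief surveys to assess state emotion, trait anger, and HAB".
- **Précis, time-point two:** "a brief self-report survey about their online (public behavior only), driving, and other behaviors over the preceding 24 hours", alongside HAB and state emotion.
- **Section 3.3, time-point one:** "a brief measure of trait (what is typical for them) aggression, and state (how they have felt recently) anger", besides the vignette task.
- **Section 3.3, time-point two:** "brief surveys asking about aggressive behaviors and state anger during the preceding 24 hour period".
- **Appendix A advertisement, part two:** volunteers will "fill out a brief questionnaire about your recent behaviors".

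Objective 4.1b (listed as primary) and hypothesis 5.2a (listed as secondary) concern how the training effect fades with delay. Both name anger and aggression.

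**The concern.** A change score needs the same quantity measured twice. Section 9.1 asks for one for aggression, while the schedule collects aggression once. An analyst following the plan would have to stop at this step and choose another outcome.

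The choice matters because several models are open: time-point-two aggression alone, the same adjusted for trait anger, or the same adjusted also for time-point-one state anger. They can give different interaction estimates. If the choice is made after the data are seen, the result for the aggression part of 4.1b and 5.2a depends on a model picked with knowledge of the outcome.

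**Working it through.** **1. The plan's own figure.** Section 7.2 gives 200 completers for 80% power at d = 0.4. With two-sided alpha 0.05, n per arm = 2(z₀.₉₇₅ + z₀.₈₀)²/d² = 2(1.960 + 0.842)²/0.16 = 98.1. That rounds up to 99 per arm, or 198 in total. The t-test version gives 99.08, which rounds up to 100 per arm, or 200. With 50% drop-out, 200/(1 − 0.5) = 400. The figures reproduce. No aggression baseline or change score enters them, so they do not depend on this point.

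**2. What is available for each half of the delay analysis (Section 8.8).**

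| Outcome | Time-point one | Time-point two | Change score |
|---|---|---|---|
| State anger (State Emotion Questionnaire) | yes, step c | yes, step k | computable |
| State aggression (Appendix F) | no | yes, step l | undefined |

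**3. Could another time-point-one item stand in?** Items asked at time-point one: 2 trait anger + 8 state emotion + 24 Angry Cognitions Scale set A + 3 demographic = 37. Appendix F holds 2 general + 7 online + 12 driving = 21 frequency items. None of the 21 is among the 37.

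**4. Is the trait form in Section 3.3 a baseline?** That section labels it aggression. The Précis, step b of 8.8 and Appendix G all identify it as trait anger: two agreement ratings about temperament. Appendix F counts acts over the past 24 hours. The items, response scale and time frame all differ, so subtracting one from the other does not measure change. Even if the label were right, a trait score is not a time-point-one value of state aggression.

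**5. Could Appendix F recover a pre-training value by recall?** No. It looks back 24 hours, and volunteers return no sooner than 24 hours after time-point one. The recall window never reaches back before training.

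**6. Is there another test of delay?** No. The mixed ANOVA and the aggression GLM in Section 9.1 do not include hours between sessions. Only the change-score regression does.

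**7. What the missing baseline costs in precision.** The documents give no correlation r between two aggression scores, so r is an assumption here. Assume also equal variances at both times, and take the time-point-two variance as 1. A baseline-adjusted model then has residual variance 1 − r², and a change score has 2(1 − r).

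| Assumed r | Time-point two only | Change score | Baseline-adjusted |
|---|---|---|---|
| 0.3 | 1 | 1.4 | 0.91 |
| 0.5 | 1 | 1.0 | 0.75 |
| 0.7 | 1 | 0.6 | 0.51 |

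These values ignore any gain from adjusting for trait anger. Using time-point two alone always loses against a baseline-adjusted model. It loses against a change score only when r exceeds 0.5.

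**The case against.** **It is an evident slip with an obvious repair.** Section 9.1 already analyses time-point-two aggression in a GLM, and adding hours and an interaction is the natural step. It also says age and gender will be covariates, so the model is not wholly open. This stands in part and lowers the weight of the point. It does not remove it: the same section ends by saying age, gender and trait measures may be used, and Section 3.3 lists education as a further control. The substitute model is therefore not determined by the text.

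**The analysis is not central.** The single primary objective in Section 3.1 does not mention duration, and hypothesis 5.2a is secondary. Only 4.1b calls it primary. This stands.

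**Section 9.5.** A reader might infer that the plan leaves the substitution to the final report. It does not: deviations may be justified in an amendment, in the report, or in both. The risk is that the text permits the later route, not that it requires it.

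**The repair does not settle everything.** This stands. Appendix F has no scoring rule and does not say how the 12 driving items count for someone who did not drive. The Angry Cognitions Scale in Appendix B, by contrast, is scored explicitly. Fixing the regression leaves that separate gap open.

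**Self-chosen return time.** A reader might infer that differences between early and late returners are harmless if they are alike in both arms. They need not be. Suppose return patterns are identical, nothing decays, and late returners simply respond less to training. The group difference then shrinks with hours although no individual effect faded. This applies to anger as well.

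**Conclusion.** The contradiction between Sections 9.1 and 8.8 is real, and the aggression half of the delay analysis cannot be run as written. One of its two outcomes is affected, and for that outcome the change score exists for 0 of up to 400 volunteers and 0 of 200 completers. It should be corrected before analysis. The conclusion rests on the Section 8.8 schedule being what is carried out, which the Précis, Section 3.3 and the advertisement all support.

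A reader might infer that the whole delay analysis fails, or that the main aggression result or the power calculation is compromised. The documents do not support this. Whichever State Emotion items make up state anger, they are asked at both time-points. The Hypothesis 1 comparison of aggression uses time-point two only, and the sample size was set without a change score. No bias in any reported estimate is shown; what is missing is an executable rule for one outcome.

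**What to change.** In Section 9.1, for aggression only, replace the change score with a regression of the time-point-two State Aggression score on group, hours since time-point one and group × hours, adjusting for trait anger, age and gender as in the existing GLM. Use the same aggression score as that GLM. Keep the change score for state anger.

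Fix the covariate set before analysis. Reconcile it with the education control in Section 3.3 and with the closing permissive sentence of 9.1, and say whether time-point-one state anger is included. In Section 3.3, change the time-point-one trait measure to trait anger. If a caveat on delay is added, limit it to this: delay is self-chosen after randomisation, so group × hours is not a randomised estimate of decay, for anger or for aggression.

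The cost is one paragraph and one word, made by a routine amendment that Section 11.3 requires to be approved before use. There are no new data and no added volunteer time. The downside is the lack of an aggression baseline, sized under the stated assumptions in step 7 of the working.

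The alternative is to give the aggression form at time-point one before training. This would make 9.1 executable as written, but only if adopted before enrolment. By the 8.8 estimates, time-point one takes (1–2) + 1 + 3 + 1 + 15 + 10 + (<1) + (<1) = 31 to 34 minutes. Another 10 makes 41 to 44, against about 30 advertised. Time-point two takes (1–2) + 10 + 3 + 10 + (<1) = 24 to 26. The total would rise from 55–60 to 65–70 minutes, against the 60 stated in Sections 3.3 and 7.1, so those sections and the advertisement would also need changing.

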## **5 HYPOTHESES**

### **5.1 Primary Hypotheses**

- a. Hypothesis 1: Relative to volunteers in the fake-training condition, those volunteers who receive the real HBMT at time-point one will report less state anger and aggression at time-point two.
- b. Hypothesis 2: Effects of HBMT on state anger and aggression in daily life will be mediated by between group differences in HAB.

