## **6 BACKGROUND AND MILITARY RELEVANCE**

### **6.1 General Background**

Aggression refers to causing harm to someone who is motivated to avoid that harm (Anderson & Bushman, 2002). Reactive or counter-aggression refers to aggression that results from being provoked or threatened as opposed to unprovoked aggression perpetrated for utilitarian goals (Dodge & Coie, 1987). However, provocations do not always result in reactive aggression. Indeed, the psychological literature is replete with examples of variables that moderate reactive aggression (See Anderson & Bushman, 2002). One key moderator is the extent to which the victim believes that the provocateur acted in an intentionally hostile manner (e.g., being shoved on purpose) versus not intending to be hostile (e.g., being shoved by mistake; De Castro, Veerman, Koops, Bosch, & Monshouwer, 2002). Hostile attributional bias (HAB) is the tendency to attribute hostile intentions to the actions of others when contextual cues are ambiguous (Milich & Dodge, 1984). Elevated HAB is observed in both reactive aggressors and premeditated aggressors. Individual differences such as trait hostility (e.g., Wingrove and Bond,

2005; Wilkowski et al., 2007) and gender (e.g., Matheson et al., 2011) are also correlated with HAB.

There are many reasons why people may attribute hostile intentions to the ambiguous actions of others. For instance, HAB is predicted by situational factors. These include exposure to real or imagine violence, such as violent video games or music (Anderson et al., 2003; Bartlett et al., 2009), social exclusion (DeWall et al., 2009), intoxication (See Osgood and Muraven, 2018), or even exposure to alcohol related information (Subra et al., 2010). Furthermore, developmental factors such as rejection from peers in childhood (Coie and Dodge, 1988) and harsh parenting (Weiss, Dodge, Bates, and Pettit, 1992), can predispose strong HAB.

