**I am a hotheaded person.**

1 = Strongly Disagree	2	3	4	5 = Strongly Agree
--------------------------	---	---	---	-----------------------

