**I have a fiery temper.**

1 = Strongly Disagree	2	3	4	5 = Strongly Agree
--------------------------	---	---	---	-----------------------

Citation: Wilk, J. E., Quartana, P. J., Clarke-Walper, K., Kok, B. C., & Riviere, L. A. (2015). Aggression in US soldiers post-deployment: Associations with combat exposure and PTSD and the moderating role of trait anger. *Aggressive behavior*, 41(6), 556-565.

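### The Hypothesis 2 mediation model leaves trait-anger control optional; if HBMT shifts HAB and level scores are used, a shared trait can produce an apparent indirect effect, above all for aggression

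*Combined protocol and SAP*

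**What the plan says.** Section 5.1 lists as a primary hypothesis: "Effects of HBMT on state anger and aggression in daily life will be mediated by between group differences in HAB". Sections 3.1 and 4.2 give the same mechanism as the secondary objective.

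The method is one sentence in Section 9.1: "Mediation analyses (if used) will be performed using non-parametric Monte-Carlo bootstrapping procedures using PROCESS". It does not say which HAB score is the mediator (set A, set B or their difference), whether the outcome is a level or a change, which covariates enter, or what is assumed about shared causes of HAB and outcome.

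On covariates, Section 9.1 says three things. Trait anger, age and gender are fixed controls in the GLM for aggression. Just before the mediation sentence, age and gender are stated as covariates without qualification. The section then closes with: "We may use age, gender, and trait measures as control variables in analyses".

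Section 6.1 names "Individual differences such as trait hostility" among the correlates of HAB. The trait measure collected is the two-item scale in Appendix G: "I am a hotheaded person" and "I have a fiery temper".

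In Section 8.8, trait anger (step b) and state emotion (step c) precede training (step e). The first HAB measure (set A, step f) and demographics (step g) follow it. HAB set B, state emotion and aggression are all taken at time-point two. HAB therefore has no pre-training value, and aggression has no time-point-one value.

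**The concern.** PROCESS builds an interval for a × b. Here a is the arm difference in HAB, and b is the slope of the outcome on HAB with arm held fixed. Randomisation protects a. It does not protect b, which is an association between two self-reports among people in the same arm. A hostile person may score high on both without one causing the other.

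The plan treats trait anger as relevant to aggression and trait hostility as related to HAB. It then leaves trait control open in the one model where randomisation gives no protection, and that choice could be made after the data are seen. The spurious indirect effect also has the hypothesised sign, since a negative a times a positive b reads as a reduction carried by HAB. At stake is the mechanism claim in Hypothesis 2. The randomised comparison in Hypothesis 1 is not affected.

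**Working it through.** **Inputs from the plan.** 100 completers per arm, planned d = 0.4, earlier immediate effect on HAB d = 0.78 (Section 7.2); alpha 0.05 (Section 9.2).

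**Assumed, because the documents give no figure.** A trait Z loads equally (L = 0.3 to 0.6) on HAB and outcome. The reliability of the trait scale is 0.5 to 1.0.

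**The plan's own figure.** n per arm = 2(1.96 + 0.842)²/0.4² = 98.1, so 99; the t-based value is 99.08, so 100. With 50% dropout, 200/0.5 = 400. Power at 100 per arm is Φ(0.4√50 − 1.96) = Φ(0.868) = 80.7%. The stated figure reproduces as a two-sided test. It powers a group difference, not the mediation test.

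**Null model.** HAB = −δG + LZ + e and outcome = LZ + e′, both with unit variance within arm. HAB has no effect on the outcome. The regression of outcome on HAB and arm nevertheless has expected slope L², which is also the within-arm correlation. The spurious indirect effect is δL² in size: at L = 0.5, 0.4 × 0.25 = 0.10 SD, or 0.78 × 0.25 = 0.195 SD.

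**Approximate rate.** The interval excludes zero roughly when both paths are significant.
- Path a: 80.7% at δ = 0.4; Φ(0.78√50 − 1.96) = Φ(3.56), about 100%, at δ = 0.78.
- Path b: Φ(atanh(L²)·√196 − 1.96), which gives 24%, 62%, 95% and 100% at L = 0.3, 0.4, 0.5 and 0.6.

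**Simulation.** Percentile bootstrap, 800 resamples, 1,500 trials per setting, 95% interval, no trait control:

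| L (within-arm r) | δ = 0.4: product | δ = 0.4: simulated | δ = 0.78: product | δ = 0.78: simulated |
|---|---|---|---|---|
| 0.3 (0.09) | 20% | 18% | 24% | 27% |
| 0.4 (0.16) | 50% | 49% | 62% | 62% |
| 0.5 (0.25) | 76% | 76% | 95% | 95% |
| 0.6 (0.36) | 81% | 80% | 100% | 100% |

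Other runs of the same model at L = 0.3 to 0.5 span 16% to 77% at 0.4 SD and 26% to 96% at 0.78 SD. With no shared trait the rate is 4% to 5%. If HBMT acts on the outcome by another route (direct d = 0.4) and HAB is inert, the rates at L = 0.5 are 77% and 94%.

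**Where the inflation disappears.**
- HBMT does not move HAB (δ = 0): at most about 5% at every loading.
- Outcome is anger change from the pre-training value: the trait covariance is L² − L² = 0; simulated 3% to 7%.
- Mediator is set B minus set A: simulated 3% to 6%, if the trait loads equally on both sets.

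**After adjusting for the trait score in both equations.** With reliability ρ, the residual HAB-outcome correlation is L²(1 − ρ)/(1 − L²ρ). At L = 0.5 and ρ = 0.8 this is 0.05/0.80 = 0.0625; at ρ = 0.6 it is 0.10/0.85 = 0.118. At δ = 0.78, where path a is almost always significant, the approximate false rates are 14% and 38%.
- Simulation at ρ = 0.8 and L = 0.3 to 0.5 gives about 6% to 17%. One set of runs had 4% at the lowest loading and smaller shift, which is no more than nominal.
- At ρ = 0.6, L = 0.5 and a 0.78 SD shift it gives 37%.
- At L = 0.5 and a 0.4 SD shift, ρ = 0.5, 0.7, 0.9 and 1.0 give 45%, 22%, 8% and 4%.

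**Power for real mediation** (b = 0.3, L = 0.5, 0.4 SD shift, ρ = 0.8): 80% to 85% unadjusted, 89% to 90% adjusted.

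**The case against.** The best reply is that the high rates assume level scores for both mediator and outcome. Section 9.1 analyses change between time-points for state anger and HAB, and a stable trait cancels in a change score. For anger this stands: with change from the pre-training value as outcome, the problem largely vanishes. It does not help aggression, which has no time-point-one value. Nor does HAB change rescue the model. Set A follows training, so B minus A measures decay rather than response. The sets also hold four and five scenarios (24 and 30 items), so summed scores would not cancel exactly. The plan does not say which scores the mediation model uses.

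Other parts of the reply also stand. The test concerns a × b, so a reader might infer that any within-arm association is enough; it is not, because HBMT must also shift HAB. A reader might infer that the plan ignores covariates. In fact it already commits to age and gender and allows trait measures; the gap is that trait control is optional and the closing sentence weakens the commitment on age and gender. The loadings and reliability are assumptions, and at L = 0.3 the rate is 16% to 28%, well short of near-certain. Finally, unmeasured shared causes affect any single-mediator analysis, and this one is marked as optional. That limits the severity, but here a relevant covariate is already collected.

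**Conclusion.** The concern holds as a conditional risk. If HBMT shifts HAB and PROCESS is run on level scores without trait control, the interval for Hypothesis 2 can exclude zero although HAB does nothing. Under equal loadings of 0.3 to 0.5 and 100 per arm, the rate is about 16% to 77% at a 0.4 SD shift and 26% to 96% at 0.78 SD. It applies above all to aggression.

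Two stronger readings are not supported. One is that anger and aggression are equally exposed: anger has a pre-training value, and using it as a change score brings the rate to 3% to 7%. The other is that trait adjustment cures the problem: with two items of unknown reliability it leaves about 6% to 17% at reliability 0.8 and up to about 37% at 0.6. An adjusted interval that excludes zero therefore does not by itself establish Hypothesis 2. The change is worth making because it is nearly free and costs no power in the setting checked.

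**What to change.** In Section 9.1, for the mediation model:

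1. Require trait anger (step b), age and gender in both PROCESS equations (HAB on arm; outcome on HAB and arm). Remove the optional wording for this model, since it conflicts with the earlier commitment on age and gender.
2. For the anger outcome, also require pre-training state anger (step c). As an addition to trait anger on level scores it gains little in simulation (13% to 11% at 0.4 SD, 16% to 14% at 0.78 SD, at L = 0.5), so it does not replace the steps below.
3. Add a sensitivity analysis giving the residual HAB-outcome correlation at which the indirect effect becomes zero.
4. Report a positive result only as consistent with mediation, conditional on no further shared causes of HAB and outcome, and always with the sensitivity result.

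The cost is SAP wording, a few lines of analysis, a few degrees of freedom and a more cautious mechanism claim. No new data are needed. Trait and state anger are collected before training; age and gender come after it (step g), which is harmless because training cannot change them.
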